This statistical analysis plan (SAP) describes the statistical methods to be used during the reporting and analyses of data collected under ADC Therapeutics (ADCT) Protocol ADCT-301-002.

This SAP should be read in conjunction with the study [protocol](#) and [case report form \(CRF\)](#).

2 Study Objectives

See the planned study objectives in the corresponding section in the protocol.

3 Study Design

Refer to the corresponding section in the protocol.

3.1 Sample Size Consideration

Refer to the corresponding section in the protocol.

3.2 Randomization

This study is not randomized.

3.3 Modifications to the statistical section of the protocol

The trial was terminated early, prior to the completion of dose escalation (part 1), therefore, only Part 1 data has been analyzed and a selected or modified analysis from the statistical section of the protocol will be performed. Please see details in each section.

4 Statistical methods

All analyses use SAS® version 9.4 or higher. Summary tables will be organized by each dose level; if some dose levels have only a few subjects, then dose levels can be combined into dose ranges. All available data will be used in the analyses, and important data will be included in data listings, sorted by dose level, subject, and by visit within subject. Missing data will not be imputed, except via censoring in survival analyses and as otherwise specified.

Unless otherwise noted, categorical data will be presented using counts and percentages, with the number of subjects in the analysis set by treatment group as the denominator for percentages. Percentages will be rounded to one decimal place, except 100% will be displayed without any decimal places, and percentages will not be displayed for zero counts. Continuous data, unless otherwise noted, will be summarized using the number of observations (n), mean, standard deviation (std), median, minimum, and maximum. Minima and maxima will be rounded to the precision of the original value, and means, medians, and confidence intervals (CIs) if presented will be rounded to 1 decimal place greater than the precision of the original value. The std will be rounded to 2 decimal places greater than the precision of the original value, up to a maximum of 3 decimal places.

No hypothesis testing will be performed in this study.

4.1 Analysis Sets

4.1.1 Safety Analysis Set

The safety analysis set consists of all subjects who receive study drug.

4.2 Subject Disposition

For the Safety analysis set, the number and percentage of subjects who discontinued study treatment and discontinued the study for each reason will be tabulated for each dose level.

Subject disposition data will be listed.

The number and percentage of patients with any important clinical study report (CSR) reportable protocol deviation will be summarized overall and by type of deviation. The pre-defined important CSR reportable protocol deviations are listed below; in addition, any other protocol deviations deemed by ADCT medical to be important CSR reportable deviations will be included in the summary.

1. Patient entered the study even though they did not satisfy the entry criteria
2. Patient received an excluded concomitant treatment
3. Patients who developed withdrawal criteria during the study but were not withdrawn.
The withdrawal criteria include:
 - Grade 3 or higher hypersensitivity reaction
 - a recurrent Grade 3 or 4 toxicity, excluding hematological toxicity
 - a protocol-defined dose-limiting toxicity (DLT) during Cycle 1

- a dosing delay >21 (except in case of potential patient benefit, which must be approved by the Sponsor) or
 - diagnosis of polyradiculopathy/GBS with the level 1 of diagnostic certainty
 - Grade ≥ 3 neurologic toxicities, defined as peripheral sensory and peripherally motor neuropathies
4. toxicity recurs at the 2nd reduced dose level and at a severity that would mandate a treatment withdrawal Patient who received the wrong treatment or incorrect dose. For example,
- actual dose of study drug was more than 15% greater than protocol defined planned dose level
 - patient started next cycle less than 18 days later after Day 1 of the most recent treatment cycle

4.3 Demographic and Baseline Characteristics

Demographic and baseline characteristics will be tabulated for the Safety analysis set.

Variables include the following:

- Sex (female, male)
- Race (white, black or African-American, Asian, American Indian or Alaska native, native Hawaiian or other Pacific Islander, other)
- Ethnicity (Hispanic or Latino, not Hispanic or Latino)
- Age (years)
- Age group (< 65, ≥ 65 - < 75, ≥ 75 years)
- Height (cm)
- Weight (kg)
- Body mass index (kg/m²)
- ECOG PS

Demographic and baseline characteristics data will be listed.

4.4 Pre-treatment disease characteristics and Medications History

Cancer history will be presented for the Safety analysis set. Cancer history will include the following variables:

- Disease diagnosis subtype (Acute myeloid leukemia (AML) or acute lymphoblastic leukemia (ALL))
- extramedullary involvement

Cytogenetic analysis will include the following variables:

For ALL:

- ALL with t(9;22)(q34;q11.2); BCR-ABL (Philadelphia chromosome)
- ALL with t(v;11q23) (MLL rearranged)
- ALL with t(1;19)(q23;p13.3); TCF3-PBX1 (E2A-PBX1)
- ALL with t(12;21)(p13;q22); ETV6-RUNX1 (TEL-AML1)
- Hyperdiploid > 50

- Hypodiploid
- t(5;14)(q31;q32); IL3-IGH
- Other

For AML:

- AML with t(8;21)(q22;q22); RUNX1/RUNX1T1
- AML with inv(16)(p13,q22) or t(16;16)(p13.1;q22);]CBFB/MYH11
- AML with t(15;17)(q22;q12)PML-RARA
- AML with t(9;11)(p22;q23): MLLT3-MLL
- AML with t(6;9)(p23;q34) DEK-NUP214
- AML with inv(3)(q21q26.2) or t(3;3)(q21;q26);RPN1-EVI1
- AML (megakaryoblastic) with t(1;22)(p13;q13): RBM15-MKL1
- AML with mutated NPM1
- AML with mutated CEBPA
- Other

All cytogenetic analysis data will be listed.

Multilineage dysplasia syndrome data will be listed.

Bone marrow evaluation (bone marrow aspirate and/or bone marrow biopsy) at screening will be listed.

Medical history will be summarized by SOC and preferred term. All medical history data will be listed.

4.5 Prior anticancer therapy

The number and percent of patients who had prior stem cell transplant and radiotherapy will be summarized.

The number of lines of prior systemic therapies will be summarized. Number of lines is derived from the unique number of regimen number reported on the prior systemic treatment CRF page and the mobilization treatment and/or conditioning treatment from the prior stem cell transplant, if appropriate.

Prior stem cell transplant, radiotherapy and systemic therapy data will be listed.

4.6 Prior or Concomitant Medications (other than anticancer therapies)

Prior and concomitant medications will be coded using the World Health Organization-Drug Dictionary (WHO-DD).

Patient listing of all prior and concomitant medications will be provided. Pre-medication for dosing (for example, prophylaxis for hypersensitivity) will listed separately.

4.7 Exposure to Treatment

4.7.1 Extent of ADCT-301 Exposure

ADCT-301 exposure will be summarized for the Safety analysis set by dose level. The following items will be tabulated.

- Duration of treatment (in weeks) = (date of last dose – date of first dose +1)/7
- Number of infusions
- Cumulative dose (in ug/kg) = sum of (dose administered at each infusion [ug] /last available weight before each infusion[kg]),
where dose administered at each infusion[ug]=concentrated IP volume [in mL]* 6 mg/mL *1000 or serially diluted IP volume[in mL]/50* 6 mg/mL *1000; for partial infusion, multiply by (1- volume of dosing solution not administered [in mL]/ 50 mL)
- Relative dose intensity (%) = (Cumulative dose / (Duration of treatment + 6/7 for QW or + 20/7 for Q3W))/ planned weekly dose intensity *100%,
where planned weekly dose intensity = planned dose level at cycle 1 day 1 for QW, or planned dose level at cycle 1 day 1 ÷ 3 for Q3W, for example, =10 ug/kg for 30ug/kg Q3W planned dose level.
For patients who switched from Q3W to QW or vice versa, the relative dose intensity is not calculated.

Relative dose intensity will be additionally presented categorized (<60%, >=60 - <80%, >=80 - <90%, >=90 - <110%, >=110%) Exposure data and infusion details will be listed together.

Exposure data will be listed.

4.7.2 Subsequent Anticancer Therapy or Procedure

Subjects' subsequent anticancer therapy or procedure including systemic therapy, radiation, transplant, or other, along with the start date of subsequent anticancer therapy or procedure will be listed.

4.8 Safety Analyses

General common rules

All safety analyses will be performed on the safety analysis set, unless otherwise specified, using the following common rules:

- The baseline value will be defined as the last non-missing value or measurement taken up to the first dose of the study drug
- The analysis of the safety variables will be essentially descriptive and no systematic testing is planned.

- If relevant, selected safety analyses may be summarized by age, sex, racial subgroups, and any pertinent subgroups.
- The toxicity grade according to the Common Terminology Criteria for Adverse Events (CTCAE) version 4.0 will be taken into account in the summary. For subjects with multiple occurrences of the same event, the maximum grade will be used. If a subject has both missing and non-missing severity grades for treatment-emergent adverse events (TEAEs) within the same preferred term (PT), the missing severity of the TEAE will be treated as a lower severity grade (ie, the subject will be counted under the non-missing severity grade).

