7.3.2.3 Reporting Adverse Events

All AEs reported or observed during the study will be recorded on the AE page of the eCRF. Information to be collected includes drug treatment, dose, event terminology, date of onset, CTCAE Version 4.0 assessment of severity, relationship to study drug, date of resolution of the event, seriousness, any required treatment or evaluations, and outcome. With the exception of disease progression, AEs resulting from concurrent illnesses, reactions to concurrent illnesses, and reactions to concurrent medications also must be reported. All AEs will be followed to adequate resolution. CTCAE Version 4.0 will be used to grade all AEs. The CTCAE includes 5 grades (1 to 5), with Grade 5 being death.

Any AE that meets SAE criteria ([Section 7.3.2.1](#)) must be reported to the contract research organization (CRO) immediately (i.e., within 24 hours after the time site personnel first learn about the event). The following contact information is to be used for SAE reporting:

Pharmacovigilance Department

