4.8.2 Adverse Events, Serious Adverse Events, and Deaths

4.8.2.1 Analyses of adverse events

The primary focus of adverse event reporting will be on the TEAEs. A TEAE is defined as an adverse event that occurs or worsens in the period extending from the first dose of study drug to 84 days after the last dose of study drug, or start of new anti-cancer therapy, whichever is earlier.

If an AE date/time of onset (occurrence, worsening, or becoming serious) is incomplete, an imputation algorithm will be used to classify the AE as pre-treatment, TEAE, or post-treatment. For example, if only the day of the AE onset is missing, the year and month will be compared with the first dose and 84 days after the last dose of study drug, or start of new anti-cancer therapy, whichever is earlier. And if the month and day of the AE onset are missing, the year will be compared with the first dose and 84 days after the last dose of study drug, or start of new anti-cancer therapy, whichever is earlier. The algorithm for imputing TEAE will be conservative and will classify an AE as a treatment emergent unless there is definitive information to determine it is non-TEAEs.

Analysis of all TEAE(s):

The following TEAE summaries will be generated for the safety analysis set.

- Overview of TEAEs, summarizing number of TEAEs and number (%) of subjects with any
 - TEAE
 - Related TEAE (including possibly related, probably related, or related)
 - Any \geq grade 3 TEAE
 - Serious TEAE
 - TEAE leading to death

- TEAE leading to permanent treatment discontinuation
- TEAE leading to ADCT-301 delay or reduction or interruption
- TEAE with at least one infusion related reaction
- All TEAEs by PT, showing number (%) of subjects with at least one TEAE, sorted by decreasing incidence of PTs
- All TEAEs by System Organ Class (SOC) and PT, showing number (%) of subjects with at least one TEAE, sorted by SOC in alphabetic order and decreasing incidence of PTs within SOC. This sorting order will be applied to all other AE tables, unless otherwise specified
- All TEAEs by SOC, PT and Maximum CTCAE grade
- All \geq grade 3 TEAEs by SOC, PT and Maximum CTCAE grade
- All related TEAEs by SOC, PT and Maximum CTCAE grade (including possibly related, probably related, or related)
- All Serious TEAEs by SOC and PT by SOC, PT and Maximum CTCAE grade

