6.1 General conventions

6.1.1 Missing data

Handling of missing relationship to investigational product of AEs

If the assessment of the relationship to investigational product is missing, then the relationship to investigational product has to be assumed and the AE considered as such in the frequency tables of possibly related AEs, but no imputation should be done at the data level.

Handling of missing severity/grades of AEs

If the severity/grade is missing for one of the treatment emergent occurrences of an AE, the maximal severity of the remaining occurrences will be considered. If the severity is missing for all the occurrences a “missing” category will be added in summary table.

No other imputation of values for missing data will be performed.

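### The SAP rule for missing adverse event grades has no provision for outcome, so an ungraded fatal TEAE can be shown below Grade 5 or as missing, and left out of the Grade 3+ table for its preferred term

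*SAP*

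**What the plan says.** Two SAP sections govern missing grades, and they agree with each other.

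- **SAP 4.8, general common rules.** Across repeated occurrences: "For subjects with multiple occurrences of the same event, the maximum grade will be used". Where one subject has both graded and ungraded TEAEs within the same preferred term, "the missing severity of the TEAE will be treated as a lower severity grade". The SAP explains this in parentheses: "the subject will be counted under the non-missing severity grade".
- **SAP 6.1.1.** If one of the occurrences has no grade, "the maximal severity of the remaining occurrences will be considered". If none has a grade, the summary table gains a category for missing severity. The section then rules out any further imputation.

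Protocol 7.3.2.3 requires every AE to be graded by CTCAE 4.0, a five-grade scale "with Grade 5 being death". It also lists outcome and seriousness among the items collected for each AE.

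Two other gaps in AE data are resolved in the cautious direction. For missing causality (SAP 6.1.1), "then the relationship to investigational product has to be assumed". For incomplete onset dates (SAP 4.8.2.1), the algorithm "will classify an AE as a treatment emergent unless there is definitive information" to the contrary.

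**The concern.** Neither missing-grade rule looks at outcome. A fatal event has a known grade by the protocol's own definition even when the grade field is blank, but the SAP does not use that information.

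The tables by maximum grade and the Grade 3+ summaries in SAP 4.8.2.1 carry much of the quantitative safety reporting. Safety is a primary objective, and after early termination efficacy and DLT data are only listed. Under the written rule one subject can be counted in the overview row for TEAEs leading to death and, for the same preferred term, stand at Grade 1 or 2 or as missing, and be absent from the Grade 3+ table. Two tables in one report would then disagree about the same event.

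Mixed records within a term are plausible. Protocol 7.3.2.4 asks for changes in severity to be documented, so a worsening event may generate more than one record.

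**Working it through.** The plan gives no figure to reproduce, so the check is a list of the cases that the rules create.

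**Inputs.** For one subject and one preferred term, let g be the highest recorded grade (1 to 5, or none) and t the true grade of the ungraded occurrence (1 to 5). By SAP 4.8 and 6.1.1 the subject is shown at g if g exists, and otherwise as missing.

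**Ungraded fatal event (t = 5).**

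| Recorded maximum g | Shown as | In the Grade 3+ table for the term? |
|---|---|---|
| none | missing | no, by implication |
| 1 | Grade 1 | no |
| 2 | Grade 2 | no |
| 3 | Grade 3 | yes, but not as Grade 5 |
| 4 | Grade 4 | yes, but not as Grade 5 |
| 5 | Grade 5 | yes |

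The first row is an inference. A missing grade does not satisfy Grade 3 or higher, and the SAP has no rule that adds it.

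**All mixed cases.** There are 5 × 5 = 25 combinations of g and t.

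- g of 3 or more: 3 × 5 = 15 combinations. The subject stays in the Grade 3+ table.
- g of 1 or 2 with t of 3, 4 or 5: 2 × 3 = 6 combinations. Grade 3+ status for the term is lost.
- g and t both 1 or 2: 2 × 2 = 4 combinations. There is no Grade 3+ event to lose.
- Check: 15 + 6 + 4 = 25.
- Within the 6, a life-threatening or fatal event sits behind Grade 1 in 1 × 2 = 2 combinations.

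**Only ungraded occurrences.** There are 5 possible values of t. All 5 go to the missing category, and none is shown as Grade 1.

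These are counts of logical cases, not probabilities. In every mixed case the tabulated grade is at or below the true maximum, so any error runs toward less severe toxicity.

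**Size in the overview row for any Grade 3+ TEAE.** One affected subject changes the proportion by 1/n, where n is the size of the dose group, and only if that subject has no other Grade 3+ TEAE under any term. Using group sizes from protocol 4.1.1:

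- n = 3: 1/3 = 33 percentage points
- n = 6: 1/6 = 17 percentage points
- n = 10: 1/10 = 10 percentage points

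Ten is the cap for a dose level unless at least 3 of the 10 patients respond. SAP section 4 also allows sparse dose levels to be combined, which makes n larger. With k affected subjects the change is at most k/n. The documents do not give k.

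**The case against.** The strongest reply is that nothing is hidden and little depends on the rule. SAP 4.8.2.1 has overview rows for serious TEAEs and for TEAEs leading to death, a serious-TEAE table, and listings of all AEs, all SAEs and all fatal TEAEs. The section on deaths summarises the reasons. Life-threatening events are serious by the definition in protocol 7.3.2.1, so they reach the serious summaries too. A missing grade is itself a data defect, and protocol 8.7 and 8.7.1 provide for completeness review and cleaning. No hypothesis is tested, DLTs are listed separately, and the steering committee, not these tables, determines the MTD.

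All of that stands, and it makes the point minor. It does not remove the conflict between tables. The serious-TEAE table is itself presented by maximum grade, so it inherits the same misplacement.

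Three stronger readings are tempting, and the documents do not support them.

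- *Any ungraded severe event becomes Grade 1.* The rule in SAP 4.8 applies only within one subject and one preferred term where a grade is also recorded. Lower there means ranked below that recorded grade. An ungraded event with no graded companion is shown as missing, which discloses the gap.
- *The plan leans toward favourable results.* The contrast with the causality and date rules is real. But those are yes-or-no choices, whereas grade has five levels and no single obvious default.
- *Every ungraded life-threatening event can be set to Grade 4 from existing fields.* The scale in protocol 7.3.2.4 is for events not included in CTCAE, and 7.3.2.3 names seriousness without showing that the individual criterion is a separate field. Only the link between death and Grade 5 is stated outright.

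**Conclusion.** The point holds in a limited form. The SAP's rule can place an ungraded fatal TEAE at a lower recorded grade or in the missing category, and leave it out of the Grade 3+ table for its term, in conflict with the protocol's definition of Grade 5 and with the row for TEAEs leading to death.

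The effect requires at least one fatal or severe TEAE to remain ungraded after cleaning; if none does, it is nil. Loss of the subject from the term's Grade 3+ table further requires that the recorded grades for that term are 1 or 2, or that there are none. The overview percentage moves by 1/n per affected subject, and only without another Grade 3+ TEAE in that subject. A reader should not infer that deaths go unreported or that dose decisions are affected. Minor priority.

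**What to change.** In SAP 4.8 and 6.1.1, ahead of the current rule, add these steps:

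1. For tabulation, an ungraded TEAE whose own recorded outcome is fatal is counted as Grade 5.
2. If, and only if, the database holds life-threatening as a separate seriousness criterion, an ungraded TEAE meeting it is counted as at least Grade 4.
3. All other ungraded TEAEs follow the existing rule.
4. The maximum-grade and Grade 3+ tables carry a footnote with the number of subjects who have an ungraded TEAE.

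The cost is a few sentences and a small derivation. Outcome is already collected; whether step 2 is possible has to be checked against the case report form. Reported severity may become slightly less favourable. If no grades are missing, the results do not change.

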4.8.1 Dose-limiting Toxicities

DLT data will be listed.

4.8.2 Adverse Events, Serious Adverse Events, and Deaths

4.8.2.1 Analyses of adverse events

The primary focus of adverse event reporting will be on the TEAEs. A TEAE is defined as an adverse event that occurs or worsens in the period extending from the first dose of study drug to 84 days after the last dose of study drug, or start of new anti-cancer therapy, whichever is earlier.

If an AE date/time of onset (occurrence, worsening, or becoming serious) is incomplete, an imputation algorithm will be used to classify the AE as pre-treatment, TEAE, or post-treatment. For example, if only the day of the AE onset is missing, the year and month will be compared with the first dose and 84 days after the last dose of study drug, or start of new anti-cancer therapy, whichever is earlier. And if the month and day of the AE onset are missing, the year will be compared with the first dose and 84 days after the last dose of study drug, or start of new anti-cancer therapy, whichever is earlier. The algorithm for imputing TEAE will be conservative and will classify an AE as a treatment emergent unless there is definitive information to determine it is non-TEAEs.

Analysis of all TEAE(s):

The following TEAE summaries will be generated for the safety analysis set.

- Overview of TEAEs, summarizing number of TEAEs and number (%) of subjects with any
 - TEAE
 - Related TEAE (including possibly related, probably related, or related)
 - Any \geq grade 3 TEAE
 - Serious TEAE
 - TEAE leading to death

- TEAE leading to permanent treatment discontinuation
- TEAE leading to ADCT-301 delay or reduction or interruption
- TEAE with at least one infusion related reaction
- All TEAEs by PT, showing number (%) of subjects with at least one TEAE, sorted by decreasing incidence of PTs
- All TEAEs by System Organ Class (SOC) and PT, showing number (%) of subjects with at least one TEAE, sorted by SOC in alphabetic order and decreasing incidence of PTs within SOC. This sorting order will be applied to all other AE tables, unless otherwise specified
- All TEAEs by SOC, PT and Maximum CTCAE grade
- All \geq grade 3 TEAEs by SOC, PT and Maximum CTCAE grade
- All related TEAEs by SOC, PT and Maximum CTCAE grade (including possibly related, probably related, or related)
- All Serious TEAEs by SOC and PT by SOC, PT and Maximum CTCAE grade

All AEs (including non-TEAEs), all SAEs (including non-TEAEs), all TEAEs leading to treatment withdrawal, all TEAEs leading to dose reduction, all TEAEs leading to dose delay, infusion related reaction and all TEAEs with fatal outcome will be listed.

In addition, neurologic AE (including the following Standardized MedDRA Queries (SMQ): Peripheral neuropathy (SMQ) [20000034], Guillain-Barre syndrome (SMQ) [20000131], and Demyelination (SMQ) [20000154]) will be listed.

4.8.2.2 Autoimmune AE, based on an ADCT specific query (includes Preferred Terms (PTs) selected based on autoimmune mediated events) will be listed. Deaths

Reasons for deaths will be summarized separately for 1) all deaths, 2) death on therapy or within 30 days after last dose of study drug.

